Measure	Variables		16-20 wks	24-30 wks	34-36 wks	1 month	4 months	9 months
Maternal Psychosocial Stress								
Perceived stress	Perceived stress Total score from PSS		1	>	>	>	>	1
Life events	Life events Total score from DLC		1	1	1	1	1	1
Depressed mood		1	1	1	1	1	1	1
Anxiety Total score from STAI		/	1	1	1	1	/	1
Maternal Stress Response								
Reactivity to TSST	Cortisol; HR, BP	>	1	>	>			
DHA Levels								
Blood draw	DHA levels in red blood cells	>	1	1	1			
Maternal Inflammatory Markers								
Blood draw	CRP; IL-6; TNF-α	>	1	>	>			
Infant Outcomes								
Birth	Birth weight, gestational age, Apgar, meconium					1		
Neurodevelopmental functioning	NBAS, BSID					1	1	1
Stress reactivity	Cortisol response to NBAS, FFSF					>	>	1
Temperament	IBQ; IBQ-R – short form						1	1

Table 1. Overview of main study variables

Hypotheses and Analyses

Hypothesis 1. DHA supplementation will improve maternal health during pregnancy among African American women living in urban poverty. Women who receive DHA supplementation will report lower levels of self-reported perceived stress over time, despite a lack of change in exposure to environmental stressors. Inflammatory markers including C-reactive protein (CRP), IL-6, TNF-α will be lower among women receiving DHA supplementation compared to placebo. To test for significant differences in perceived stress and inflammatory marker levels we will use repeated measures ANOVA (rmANOVA) with supplement group as the between-subjects factor and visit as a within-subjects factor. The interaction between group and time will be of particular interest. A Greenhouse-Geisser sphericity adjustment (Geisser & Greenhouse, 1958) will be employed. If any of the dependent measures exhibit a non-normal distribution (e.g. CRP), then a suitable data transformation will be used. Changes over time in prenatal levels of depression and anxiety will also be assessed using rmANOVA. Scatter plots and box plots of the data will be used to further explore these relationships. Plots of the data also will be examined to detect nonlinear time effects in addition to using orthogonal polynomial contrasts to formally test for quadratic and cubic effects. The association between change in DHA levels in the blood from baseline to the last prenatal visit and change in perceived stress will be examined using linear regression models.

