Response to a controlled stressor including cortisol, blood pressure, and heart rate will be better modulated among women receiving DHA supplementation than among women who do not, as demonstrated by a lower peak response and more rapid recovery to baseline. Differences in stress reactivity (i.e., cortisol levels, blood pressure, and heart rate) will be tested using two complementary approaches. First, we will use rmANOVA with supplement group as the between-subjects factor and timing of measurement (e.g. 20 minutes and 5 minutes pre-TSST, and 20, 40, and 50 minutes post-TSST for cortisol) as the within-subjects factor for each of the 4 prenatal visits separately. The interaction between group and time will be tested. For further interrogation of these changes, a random intercept, random slope mixed-effects model will be fit and results compared to the rmANOVA results. Second, the area under the curve (AUC) will be calculated for each participant at

each visit. Since primary interest is in assessment of changes over time, the AUC_I (area under the curve with respect to increase) will be used (Pruessner et al., 2003). Differences in these AUCs will be tested using rmANOVA with supplement group as the between-subjects factor and visit as the within-subjects factor. The interaction between group and visit will also be included to explore whether the magnitude of the difference between the groups is affected by the length of DHA supplementation. A Greenhouse-Geisser sphericity adjustment will be employed in both rmANOVA analyses. For further exploration of the patterns over time, a cluster analysis using the AUCs at each visit will be performed, and the association between the "change groups" formed from this cluster analysis and supplement group will be determined using a chi-square or Fisher's exact test. Log-transformed cortisol values will be used if appropriate. Also, time of collection and prenatal depression and anxiety will be controlled for in these analyses if needed.

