Power Calculations for Hypothesis 1. In this study with 108 participants in the supplement group and 54 in the placebo group, there will be >90% power to detect a difference in stress levels, at any particular visit, of the same magnitude as that observed in our preliminary study at 30 weeks (27.5+/-3.4 vs. 29.3+/-3.1), using a two-sided test at the 0.05 significance level. Additionally, with 162 participants, there will be 80% power to detect a correlation of 0.22 between changes in DHA levels in the blood versus changes in perceived stress. For the cortisol response to the TSST, there will be >95% power to detect a difference in AUCs at a given visit of the same magnitude as that found in our preliminary study at 30 weeks (-4.5+/-3.9 vs. -8.1+/-6.1; negative values indicating net decreases rather than increases), using a two-sided test at the 0.05 significance level.

Hypothesis 2. DHA supplementation during pregnancy will improve infant birth and developmental outcomes among African American women living in urban poverty.

Infants of mothers who receive DHA supplementation will have longer gestations, higher birth weights, more optimal neurodevelopmental outcomes as measured by the NBAS and Bayley Scales of Infant Development, and more optimal maternal reports of temperament in comparison to infants whose mothers did not receive DHA supplementation. We will use ANOVA (e.g. birth weight) or rmANOVA (e.g. NBAS) to test for significant differences between treatment groups. For categorical infant outcomes, such as pre-term birth or low Apgar scores, logistic regression will be employed. We will also test the association between level of DHA in blood at the last prenatal visit and/or change in DHA levels from baseline and infant outcomes using linear (e.g. birth weight or change in NBAS) or logistic (e.g. pre-term birth) regression.

Transformations of the continuous dependent measures will be performed to stabilize the variance across groups if needed.

Infants of mothers who received DHA supplements will demonstrate more modulated cortisol response to the NBAS and still-face paradigm, with a lower peak response and a steeper slope from peak to recovery, in comparison to infants whose mothers did not receive DHA supplementation. Analyses will be performed as described for Hypothesis 1.

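### Hypotheses 1 and 2 are each tested on many outcomes with no primary outcome, decision rule or multiplicity control, so nothing prevents a claim of support resting on one chance result

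*Combined protocol and SAP*

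**What the plan says.** Under Hypotheses and Analyses, Hypothesis 1 is a general claim of better maternal health. Its predictions cover perceived stress and three blood markers ("Inflammatory markers including C-reactive protein (CRP), IL-6, TNF-α will be lower among women receiving DHA supplementation compared to placebo"), each analysed by one repeated-measures ANOVA across visits. Depression and anxiety are assessed in the same way. Cortisol, blood pressure and heart rate in response to the Trier Social Stress Test (TSST) are then analysed in two ways: by a repeated-measures ANOVA "for each of the 4 prenatal visits separately", and by an area-under-the-curve (AUC) analysis across visits. A mixed model and a cluster analysis are added.

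Hypothesis 2 covers gestation, birth weight, preterm birth, Apgar, NBAS, Bayley, maternal reports of temperament, and infant cortisol at 1, 4 and 9 months. Infant cortisol is to be handled as under Hypothesis 1.

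Each group comparison in the power paragraphs is sized "using a two-sided test at the 0.05 significance level", with "108 participants in the supplement group and 54 in the placebo group". Five are sized: perceived stress and cortisol AUC for Hypothesis 1, and ICQ, still-face (FFSF) cortisol and birth weight for Hypothesis 2. For perceived stress, "there will be >90% power to detect a difference in stress levels, at any particular visit". The analysis paragraphs state no significance level. The word primary is used for the interest in change over time and for the intent-to-treat analysis, never for an outcome.

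**The concern.** A 0.05 level limits the error of one test. It does not limit the error of a hypothesis that can be supported through any of a dozen or more tests. With no outcome ranked first and no rule for what counts as support, whichever result reaches 0.05 can be presented afterwards as support for the whole hypothesis.

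This matters here because the trial is presented in part as a replication. In the pilot, perceived stress and cortisol differed at 30 weeks but not at baseline or 24 weeks. A replication is most convincing when the outcome and visit that decide it are fixed beforehand.

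**Working it through.** **1. The plan's own power figures.** Inputs from the power paragraphs: 108 and 54 women, two-sided 0.05. The standard error is the pooled SD × √(1/108 + 1/54) = pooled SD × 0.1667.

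- Perceived stress ("27.5+/-3.4 vs. 29.3+/-3.1"): pooled SD = √[(107×3.4² + 53×3.1²)/160] = 3.30; SE = 0.551; difference 1.8; ratio 1.8/0.551 = 3.27. Power from the noncentral t with 160 df is 90.1% (stated: above 90%).
- Birth weight (3174±480 vs 2889±549 g): pooled SD = 503.9; SE = 83.98; difference 285; ratio 3.39. Power is 92.1%, or 89.5% allowing unequal variances (stated: about 90%).

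The stated powers for cortisol AUC, ICQ, FFSF cortisol and the correlation of 0.22 also reproduce. Each is right for a single test.

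**2. Counting the tests.** Only post-baseline tests of predicted effects are counted.

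- Hypothesis 1: perceived stress and three markers (4) + three reactivity measures × three post-baseline visits (9) + three AUC analyses (3) = 16.
- Hypothesis 2: gestation, birth weight, preterm birth, Apgar, NBAS, Bayley, ICQ, IBQ-R (8) + infant cortisol at three ages (3) = 11.

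The counts leave out depression and anxiety, separate systolic and diastolic pressure, subscales, polynomial contrasts, regressions on DHA level, the mixed model and the cluster analysis.

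**3. Chance of at least one p<0.05 when there is no effect.** With k independent tests it is 1 − 0.95^k: 1 − 0.95^16 = 0.56 and 1 − 0.95^11 = 0.43. For favourable results only, 0.975 replaces 0.95.

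For equally correlated tests with correlation ρ it is 1 − ∫ p(u)^k φ(u) du. Here p(u) = Φ((1.96 − √ρ·u)/√(1−ρ)) − Φ((−1.96 − √ρ·u)/√(1−ρ)). The second term is dropped for favourable results only. The documents give no outcome correlations, so ρ is an assumption.

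| | Independent | ρ = 0.3 | ρ = 0.5 | ρ = 0.8 |
|---|---|---|---|---|
| Hypothesis 1, 16 tests, either direction | 56% | 48% | 37% | 21% |
| Hypothesis 1, favourable only | 33% | 24% | 19% | 10% |
| Hypothesis 2, 11 tests, either direction | 43% | 37% | 30% | 18% |
| Hypothesis 2, favourable only | 24% | 19% | 15% | 9% |

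The nominal values for one test are 5% and 2.5%.

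**4. Price of the remedies** (noncentral t, as in step 1).

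| Rule | Perceived stress | Birth weight |
|---|---|---|
| One primary per hypothesis at 0.05 | 90% | 92% |
| One primary per hypothesis at 0.025 | 84% | 87% |
| Bonferroni over all tests of the hypothesis (0.05/16 = 0.0031; 0.05/11 = 0.0045) | 61% | 70% |

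Two primaries at 0.05 each leave 1 − 0.95² = 9.75% across the two hypotheses if independent, and at most 10%. At 0.025 each the total is at most 5%.

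**The case against.** Several points on the other side stand.

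- A reader might count every planned test: six repeated-measures outcomes, three reactivity measures at four visits and three AUC analyses, 21 in all, giving 1 − 0.95^21 = 66%. That overstates the case. A baseline difference cannot support a treatment effect, and improvement in depression and anxiety is not predicted. Independence is also implausible, because the AUC analyses reuse the per-visit data from the same women. A range is the honest figure.
- The predictions are directional, so an unfavourable result would not be reported as support. The favourable-only rows allow for this, and they remain well above 2.5%.
- A reader might infer that the plan treats one significant result as enough. It does not say so. It gives no decision rule, and 0.05 per test is inferred from the power paragraphs. The defect is that the plan does not exclude that reading.
- A reader might also infer that the trial cannot confirm the pilot findings. The documents do not support this. The trial is sized on pilot values for perceived stress, cortisol AUC and birth weight, and measuring other outcomes does not invalidate a test of any of these. What lacks protection is the claim for the broad hypothesis.
- The power section does not favour perceived stress or birth weight over the other outcomes it sizes. The choice belongs to the sponsor.

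**Conclusion.** The concern holds in this form: two broad hypotheses, many outcomes, and no primary outcome, decision rule or multiplicity control. If supplementation has no effect, at least one p<0.05 would be expected with probability 21-56% for Hypothesis 1 and 18-43% for Hypothesis 2. For favourable results alone the ranges are 10-33% and 9-24%. The ranges run from an assumed common correlation of 0.8 to independence, and rest on 0.05 being applied to each test and on the counts of 16 and 11. The plan's power figures are not in question. The point should be settled before unblinding. It does not invalidate the design.

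**What to change.** - Before unblinding, name one primary outcome and one contrast for each hypothesis, chosen from the group comparisons already sized, and justify the choice. Perceived stress at the last prenatal visit and birth weight would serve; cortisol AUC (Hypothesis 1) and ICQ or FFSF cortisol (Hypothesis 2) are the alternatives. If perceived stress is chosen, state whether the single-visit comparison or the group-by-time interaction decides. The power statement covers the single-visit comparison, and assumes that the 30-week pilot difference applies at the chosen visit.
- State that a hypothesis is supported only on its primary. Label all other outcomes secondary or exploratory.
- Do not count the baseline-visit reactivity test as evidence of effect. Replace the four per-visit tests with one: either the cross-visit AUC analysis already planned, naming the term that decides, or one prespecified contrast at the last prenatal visit.
- State the level. Using 0.05 per primary controls each hypothesis at 5% but leaves up to about 10% across the two. If trial-wide control is wanted, use 0.025 each.

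The cost is protocol wording. No data or planned measurements are lost, power at 0.05 is unchanged, and 0.025 each costs about 5 to 6 percentage points. Secondary findings would be claimed more cautiously. Bonferroni over all tests is not advised, given its loss of power.

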In addition to associations between DHA supplementation and prenatal stress, we observed significantly higher birth weights among neonates born to women receiving DHA compared to placebo controlling for gestational age (3,174 grams versus 2,889 grams, p = .018) and greater likelihood of having a 1-minute Apgar score of 9 (odds ratio = 5.99 [95% Cl = 1.25 - 28.75], p = .025, controlling for birth weight and gestational age). Finally, 13% of neonates of mother receiving DHA supplementation were born prior to 37 weeks, compared to 22% of mothers received placebo; a difference that did not reach the level of statistical significance in the pilot study, but is clinically meaningful.

In summary, the data from our preliminary study are compelling in terms of the potential impact on health disparities in maternal and infant health, a significant public health problem that is poorly understood. We now seek to expand on these preliminary findings by conducting a more rigorous assessment of prenatal DHA supplementation on maternal and infant health by increasing the number of participants to 162, beginning supplementation earlier in pregnancy, adding additional measures of maternal health and stress response during pregnancy, increasing the frequency of assessment, assessing DHA levels in red blood cells at each visit, and including multiple postnatal assessments of infant neurodevelopment. The proposed study offers an opportunity for replication and to test the impact of supplementation on infant functioning and, if effects are observed, whether they are mediated by changes in prenatal stress.

APPROACH

Participants

One hundred-sixty-eight pregnant, African American, women will be recruited from the University of Chicago obstetric clinic. Inclusion criteria will include: age between 18 and 34 years, household receipt of public assistance (e.g., Medicaid insurance) due to low-income, and low levels of DHA consumption as defined as less than two fish servings per week. Exclusion criteria are reports of known medical complications, regular use of steroid medications, alcohol, cigarettes, or illegal substances (by maternal report), use of blood thinners or anti-coagulants, use of psychotropic medications, BMI >40, and allergy to iodine and/or soy. Participants may be excluded if medical complications arise after enrollment. Neonates with significant medical complications will be maintained in the study.

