There are two reasons for our focus on African American women. First, as described above, African American women are disproportionately represented among families living in inner-city poverty and have the highest rates of suboptimal birth outcomes in the U.S. (Giscombé & Lobel, 2005). Second, there are racial differences in cortisol reactivity to

stress and pregnancy (De Santis et al., 2007; Glynn et al., 2007; Wilcox et al., 2005) and in the genes regulating cortisol (Baerwald et al., 1999). Given the scope of the proposed study and the potential to generate data that can be translated into reductions in health disparities, we chose to study African Americans only, but acknowledge that it will be important to test racial and ethnic differences in maternal and infant response to DHA supplementation during pregnancy.

Women will be randomly assigned to receive the omega-3 nutritional supplement (n = 112) or a corn and soybean oil placebo (n = 56) beginning at enrollment and up through the end of pregnancy. In the proposed design we allocate the number of participants to groups to optimize power to test the hypotheses. We expect greater variability in the independent measure (i.e. DHA level) and dependent measures (e.g., stress reactivity) in participants in the experimental group than those in the control group given anticipated differences in uptake and metabolism. Thus, we plan to enroll a higher number of participants in the experimental group than in the control group to adequately capture that variability (Cox, 1958). Participants and investigators will be blinded to the group to which they have been assigned. Treating clinicians will identify demographically eligible participants who will be contacted by research staff for further screening. Participants who meet the inclusion and exclusion criteria will then be scheduled for the baseline visit.

Participants will be reimbursed on an accelerated schedule with \$100 for their first visit and an increase in payments by \$25 for each subsequent visit, ending with a \$250 payment for the last post-partum visit. Participants will receive incentives in between visits including water bottles, tote bags, newborn t-shirts, etc. They also will be reimbursed with \$10 to cover travel costs for each visit.

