Nordic Naturals adheres to high standards on safety and purity by setting low levels of allowances for peroxides, heavy metals, dioxins, furans, and PCBs. A certificate of analysis is provided for every batch of ProDHA based on both an internal analysis and an analysis conducted by an independent laboratory.

The investigational pharmacy at the University of Chicago will use computer generated random assignment of ID numbers to active supplement or placebo in blocks of 18: 12 ID numbers will be randomized to active supplement and six to placebo. In order to maintain the double-blind, the pharmacist will divide each randomization block of 18 ID numbers into groups of three: six ID numbers were assigned to group A (placebo) and the remaining 12 will be assigned to either group B or C, both of which will receive identical doses of active supplement. This approach will allow the pharmacist to randomize on a 2:1 ratio without having the unbalanced design break the blind. Once the study is complete and the blind broken, the two groups receiving identical doses of active supplement will be combined for analyses.

Each participant will receive a 6-week supply. She will bring any unused DHA back to her next visit; pills will be double counted at that time as an additional method for monitoring compliance. At each visit she will receive the next supply. Research assistants will contact participants by phone 3 times per week to ask the time of day that supplement was taken, and data on perception of taste, and possible gastrointestinal side effects. At each laboratory visit research assistants will interview participants about diet over the past 24 hours and past two weeks to determine intake of sea fish or other DHA rich foods (e.g., flax seed).

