Assuming a start date of July 2015, our goal would be to begin recruitment in October 2015. Using an escalating/de-escalating recruitment design, 6 participants would be recruited each month for a period of 8 months, 4 participants per month for 6 months, and then 2 participants per month for 8 months. The recruitment rate would then accelerate again to 4 participants per month for 6 months and then 6 participants per month for 8 months. This design allows us to conduct approximately 21 sessions per month or 5 participants per month on average and complete data collection by January of 2020.

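### The enrolment total is contradictory (168 randomised, 162 used for power, a schedule that sums to 160), no loss allowance is stated, and the powers at 162 have almost no reserve

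*Combined protocol and SAP*

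**What the plan says.** All three totals stand in the current text of the combined protocol and SAP.

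- **162.** The summary that closes *Preliminary support for hypotheses* speaks of "increasing the number of participants to 162". The power sections for Hypotheses 1 and 2 use the matching split, beginning with "In this study with 108 participants in the supplement group and 54 in the placebo group, there will be >90% power". The correlation and mediation powers also use 162.
- **168.** *Participants* opens with "One hundred-sixty-eight pregnant, African American, women will be recruited" and continues: "Women will be randomly assigned to receive the omega-3 nutritional supplement (n = 112) or a corn and soybean oil placebo (n = 56".
- **160.** *Timeline for participant visits* begins with "6 participants would be recruited each month for a period of 8 months, 4 participants per month for 6 months". A slow stretch of eight months at two a month comes next, and the last part reads: "The recruitment rate would then accelerate again to 4 participants per month for 6 months and then 6 participants per month for 8 months".

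Under *Nutritional Supplement*, IDs are randomised "in blocks of 18: 12 ID numbers will be randomized to active supplement and six to placebo".

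*Missing data* says missingness should not be a major problem, citing pilot retention. It plans last observation carried forward (LOCF) with a complete-case sensitivity analysis. The pilot report gives 4 withdrawals among 64 women (6.3%), and 47 of 64 (73.4%) attending all three sessions.

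**The concern.** A trial needs one enrolment target that the recruitment plan, the randomisation list and the power calculation all share. Here they do not share one, and nothing says whether 162 is the number enrolled or the number expected to contribute data. If 162 is the evaluable number, the plan should say what loss was assumed. If it is the enrolled number, the powers assume no loss at all, in a study with four prenatal visits and three more up to 9 months after birth.

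At stake is how a non-significant PSS, ICQ, FFSF or DHA–stress correlation result will be read. A reader will take the stated 80% or 90% at face value, so the margin behind those figures matters.

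**Working it through.** **1. Totals.** Participants: 112 + 56 = 168. Power sections: 108 + 54 = 162. Timeline: 6×8 + 4×6 + 2×8 + 4×6 + 6×8 = 48 + 24 + 16 + 24 + 48 = 160, over 36 months. The schedule is 8 short of 168 and 2 short of 162.

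**2. Reproducing the stated powers at 108/54** (two-sided 0.05). For two means, the noncentrality is δ = Δ / (s·√(1/n₁ + 1/n₂)) with n₁ + n₂ − 2 degrees of freedom. Here √(1/108 + 1/54) = 1/6.

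- PSS: Δ = 29.3 − 27.5 = 1.8. Pooled s = √[(107×3.4² + 53×3.1²)/160] = 3.304, so δ = 1.8/0.5506 = 3.269 and power is 90.1% (stated: above 90%). Welch gives 91.7%.
- ICQ: δ = 3.7/(7.8/6) = 2.846, power 80.8% (stated 80%).
- FFSF: δ = 0.19/(0.4/6) = 2.850, power 80.9% (stated 80%).
- r = 0.22, N = 162, Fisher z: atanh(0.22)×√159 = 0.2237×12.61 = 2.820; 2.820 − 1.960 = 0.860; power 80.5% (stated 80%).

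All four reproduce.

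**3. Reserve.** The fully observed number at which power falls to the stated level depends on the method, which the plan does not name:

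- PSS: 161–162 (pooled), 157 (average variance), 153 (Welch).
- ICQ and FFSF: 158–159 (t), 157 (normal approximation).
- r = 0.22: 160 (Fisher z), 157 (noncentral t).

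**4. Loss at the pilot withdrawal rate.** 4/64 = 6.25%. The gap between the two stated sizes is (168 − 162)/168 = 3.6%. After pilot withdrawal, 168 leaves 168×0.9375 = 157.5, about 157; 162 leaves 151.9, about 152.

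| Observed (split) | PSS pooled / Welch | ICQ | FFSF | r = 0.22 |
|---|---|---|---|---|
| 162 (108/54) | 90.1 / 91.7% | 80.8% | 80.9% | 80.5% |
| 160 (107/53) | 89.7 / 91.3% | 80.1% | 80.3% | 80.0% |
| 157 (105/52) | 89.1 / 90.8% | 79.4% | 79.5% | 79.3% |
| 152 (101/51) | 88.3 / 90.0% | 78.3% | 78.4% | 77.9% |

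At 157, the differences detectable with 80% power are ICQ 3.73, FFSF 0.191 and r 0.222, against 3.7, 0.19 and 0.22 in the plan.

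**5. A larger loss, as illustration only.** The pilot's 30-week tests imply how many women were analysed. F[1,47] with group and two covariates gives 47 + 4 = 51. The cortisol test gives 83.85/1.78 + 2 ≈ 49. These are 79.7% and 76.6% of 64, or 134 and 129 of 168. With that many complete cases, ICQ, FFSF and r would have about 71–73% power, and PSS 82.5–84.1% (pooled) or 84.5–86.0% (Welch). Under the planned LOCF at 112/56, assuming an unchanged SD, PSS power would be 72–75% if carried values held none of the effect, 83–84% if half, and 91% if all.

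**6. Endpoints with room.** The area-under-the-curve comparison keeps its stated 95% down to about 139 observed (Welch). Birth weight, stated at about 90%, has 91.2% (pooled) or 88.4% (Welch) at 157.

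**7. Blocks.** 162/18 = 9 whole blocks; 168 = 9×18 + 6. The text does not say how the last 6 IDs are assigned.

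**The case against.** The strongest reply is that the mismatch hardly matters. The powers are right at 162. Even with 168 enrolled and pilot withdrawal, PSS by Welch stays above 90%, and the other three come within about a point of 80%, or reach it under a normal approximation or noncentral t. The plan names no method, so 160 is not a hard threshold. All of this stands.

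A reader might go further and infer that the infant outcomes are really powered at about 70%. The documents do not support that. The 77–80% analysed fraction is deduced from error degrees of freedom at one prenatal pilot visit. It is not a reported attendance rate, and no postnatal rate is given. Nor is 82–86% for PSS the planned analysis: it is a complete-case figure, whereas LOCF comes first in the plan.

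Two further inferences are also weak. The Timeline's figure of about 21 sessions a month does not single out 160: seven visits over 52 months give 160×7/52 = 21.5 and 162×7/52 = 21.8. Ending on a partial block is routine, and its effect on power is negligible.

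None of this reconciles the three totals or supplies the missing allowance. If the 168-to-162 gap is an unstated allowance, it is smaller than the pilot's own withdrawal.

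**Conclusion.** The enrolment total is wrong as written. Three figures (168, 162, 160) stand unlinked, and the recruitment schedule reaches neither stated size. The stated powers are not miscalculated, but they assume at least about 157–162 fully observed women or infants (about 153 for PSS by Welch), and no allowance is given.

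If loss is near pilot withdrawal and 168 are enrolled, the cost is about one percentage point, which is minor. If only 162 are enrolled, the same withdrawal costs about two to three points. Anything larger rests on an assumed loss rate, and on how much of the effect carried-forward values retain. Applying the pilot's withdrawal rate to this trial is itself an assumption, because follow-up here runs to 9 months after birth. Mediation power was not recomputed.

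**What to change.** 1. State one enrolment total in the pilot summary, *Participants* and *Timeline*, and label 162 as enrolled or evaluable.
2. Make the schedule sum to that total. For 168, add 8 recruits, for example 3 rather than 2 a month in the slow 8 months. For 162, add 2.
3. If 168, specify a final block of 6 with two IDs in each of groups A, B and C. That gives 9×12 + 4 = 112 and 9×6 + 2 = 56, and keeps the three-group masking.
4. Restate the PSS, ICQ, FFSF and correlation powers, or the detectable differences, at the number expected to be observed. Label the loss assumption: at least pilot withdrawal, about 157 of 168. Rerun the mediation power at the same number.

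The cost is recalculation and text edits. Keeping 168 adds 8 women to the schedule but none to the stated target, and no enrolment beyond 168 is needed. The downside is slightly less favourable stated figures.
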